#### 8.4.4 EVENTS OF SPECIAL INTEREST

AEs of special interest are listed in Section 8.1.

---

#### 8.4.5 REPORTING OF PREGNANCY

1. All FCBP are screened for pregnancy at the screening visit, and subsequently managed as mandated by the pomalidomide REMS. The REMS has the following requirements for pregnancy screening throughout the study.
2. Females taking Pomalidomide must avoid pregnancy during active treatment and for at least four weeks after taking pomalidomide.
3. Female patients of reproductive potential must either completely abstain from heterosexual sexual contact or must use two effective methods of contraception (at least one highly effective method and one effective method) at the same time (see Table 2 below).
4. The 2 effective contraceptive methods include using at the same time at least 1 highly effective method and at least 1 additional method of birth control every time they have sex with a male.

5. The 2 effective contraceptive methods must be started at least 4 weeks before POMALYST therapy, during therapy (including dose interruptions), and for at least 4 weeks following discontinuation of therapy.
6. The subject will undergo pregnancy testing twice prior to pomalidomide initiation. They must obtain a negative pregnancy test 10 to 14 days before first study drug order and again within 24 hours before study drug order even if continuous abstinence is the chosen method of birth control.
7. Pregnancy testing must occur weekly during the first four weeks of use.
8. During subsequent cycles, pregnancy testing must occur every 4 weeks if they have regular menses or every two weeks if menses are irregular.
9. The sensitivity of the pregnancy test should be at least 50mIU/ml.
10. Since oral estrogen may have a potential therapeutic effect in HHT, oral contraceptives are not considered an acceptable means of contraception during this study.

Table 2. REMS Program Contraceptive Methods		
Highly Effective Methods	Additional Effective Methods	Unacceptable Methods

 
• Intrauterine device (IUD)
 
• Hormonal methods: 
 
- Hormonal patches
 
- Injections
 
- Vaginal rings
 
- Implants
 
 
 
• Tubal ligation
 
• Partner's vasectomy
 
	
 
• Male latex or synthetic condoms
 
• Diaphragm
 
• Cervical cap
 
	
 
• Progesterone-only “mini-pill”
 
• IUD progesterone T
 
• Female condoms
 
• Natural family planning (rhythm method)
 
• Breastfeeding
 
• Fertility awareness
 
• Withdrawal
 
• Cervical shield*
 

\*A cervical shield should not be confused with a cervical cap which is an effective secondary form of contraception.

Pomalidomide is present in semen of males taking the drug and therefore males must always use a latex or synthetic condom during any sexual contact with females of reproductive potential while taking pomalidomide and for up to 4 weeks after discontinuing pomalidomide, even if they have undergone a successful vasectomy. Male patients taking pomalidomide must not donate sperm.

Study subjects must not donate blood during treatment with pomalidomide and for 1 month following discontinuation.

Pregnancies and suspected pregnancies (including a positive pregnancy test regardless of age or disease state) of a female subject occurring while the subject is on pomalidomide, or within at least 28 days of the subject's last dose of pomalidomide, are considered reportable events. Pomalidomide is to be discontinued immediately. The pregnancy, suspected pregnancy, or positive pregnancy test must be reported to the DCC and institutional IRB (as applicable) as an SAE. The subject should be referred to an obstetrician-gynecologist, preferably one experienced in reproductive toxicity for further evaluation and counseling. The Investigator will follow the female subject until completion of the pregnancy, and must notify the DCC and institutional IRB (as applicable) about the outcome of the pregnancy (either normal or abnormal outcome) within 15 days.

All neonatal deaths that occur within 28 days of birth should be reported, without regard to causality, as SAEs. In addition, any infant death after 28 days that the Investigator suspects is related to the in utero exposure to the pomalidomide should also be reported to the DCC and institutional IRB (as applicable) within 24 hours of the Investigator's knowledge of the event using the SAE Report Form.

If a female partner of a male subject taking investigational product becomes pregnant, the male subject taking pomalidomide should notify the Investigator, and the pregnant female partner should be advised to call their healthcare provider.

## 8.5 STUDY HALTING RULES

Randomization of new participants will be halted when eight thromboembolic events, defined as any venous thromboembolic event requiring medical intervention (grade 2 or higher) or any arterial thromboembolic event, that are determined to be related or "probably related" to the study drug are reported to the DCC.

The DCC will notify the study monitor, study sponsor, PI and investigators immediately when the eighth thromboembolic event (as defined above) is reported and randomization functionality will be deactivated. The PI will inform the DSMB members within 24 hours of this occurrence and the DCC will provide the DSMB with AE listing reports. The DSMB will convene an ad hoc meeting by teleconference or in writing as soon as possible. The DSMB will provide recommendations for proceeding with the study to the study sponsor/NIH. The clinical coordinating center will inform NHLBI and the FDA of the temporary enrollment halt and the disposition of the study.

## 8.6 SAFETY OVERSIGHT

This study will be reviewed for safety by an independent data safety monitoring board (DSMB) who are familiar with HHT, selected by NHLBI (per protocol), work independently of the PI, and thus have the appropriate expertise to monitor the safety and risk/benefit ratio of pomalidomide for HHT. Serious adverse events that arise in this study will be brought to the attention of the PI, DCC, IRB, FDA, NHLBI, and Celgene. The DSMB will meet every 6 months during the study. Two meetings will include a planned interim analysis for efficacy or futility after 50% and 75% of subjects have completed the 24 week treatment period. See section 10.4.7 for further details.

## 9 CLINICAL MONITORING

Site monitoring visits will be conducted by the Data Coordinating Center to inspect study data, informed consent forms, subjects' medical records, and Case Report Forms, pursuant to US GCPs and other federal and local regulations. Monitoring visits will occur in the first year after site activation and every other year thereafter. The study site principal investigator will permit authorized representatives of the FDA, NHLBI, and local health authorities to inspect relevant facilities and records.

## 10 STATISTICAL CONSIDERATIONS

### 10.1 STATISTICAL AND ANALYTICAL PLANS

A detailed statistical analysis plan (SAP) will be prepared by the study statistician and approved by the trial Steering Committee and the DSMB prior to database lock and unblinding of the study data. Details of all analyses including data reduction steps, calculation of derived variables, primary, secondary, subgroup, and confirmatory analyses will be provided in the SAP. The SAP will have table templates as appropriate. The SAP will also fully specify the criteria to make decisions at the interim and final analyses, including:

- Definition of the endpoint(s) that will be considered when deciding if the trial should continue beyond the pre-planned interim analysis. These endpoints will include the primary efficacy and safety endpoints, but may also include other outcome measures.
- Decision criteria. The rules that pre-specify the criteria for recommending that the trial stop at the interim analysis. The decision criteria will be specified using established methods for group sequential trial design that will assure that the pre-trial statistical operating characteristics are not altered by the interim analysis.
- Methods for implementing the interim analyses: often the pre-trial timing of the interim analysis must be altered to accommodate differences from the pre-trial assumptions about event rates and timing of DSMB meetings. The SAP will pre-specify the procedures that will be used to modify the decision rules to accommodate changes in the timing of the interim analysis.
- Bias-adjusted inference: the SAP will specify the method for reporting of trial results that will adjust for the bias that is introduced by the interim analysis.

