7 STATISTICAL/ANALYTICAL ISSUES

7.1 General Rules

All statistical computations will be performed, and data summaries created using SAS 9.4 or higher. For summaries of study data, categorical measures will be summarized in tables listing the frequency and the percentage of subjects in each study arm; continuous data will be summarized by presenting mean, standard deviation, median and range; and ordinal data will be summarized by presenting median and range.

Estimates from linear models will be presented by mean, standard error, and 95% CI. Estimates from logistic regression will be presented by odds ratios and 95% CIs. All statistical tests will be 2-tailed.

Checks of assumptions (e.g., normality) underlying statistical procedures will be performed and corrective procedures such as use of a transformation or application of nonparametric tests will be applied.

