7.7 Multiple Comparisons and Multiplicity

For inferential tests, the p-value for determination of statistical significance (Type I error) for the single primary efficacy outcome (change in ESS from baseline to week 24) will be evaluated relative to 0.044 to adjust for the interim efficacy analysis (see Section 9.6). However, the 75% interim analysis was conducted at 80% due to timing of DSMB meetings. This changed the significance level for the primary outcome from 0.044 to **0.0425** (see Appendix 3).

Significance of the treatment group comparison for 5 key secondary outcomes will be evaluated as follows: If the primary endpoint is found statistically significant at $p < 0.0425$, then the key secondary endpoints will be evaluated for statistical significance with a Hochberg modification to the Bonferroni adjustment (Hochberg, 1988), in which the p-values of the 5 outcomes will be ordered. The largest p-value will be compared relative to $p < 0.05$, and if met, all 5 endpoints will be considered significant. If not, then the second largest p-value will be assessed relative to $p < 0.05/2 = 0.025$, and if met then it and the other three endpoints will be considered significant, and so on for the third p-value compared at $0.05/3 = 0.017$, the fourth compared to $0.05/4 = 0.012$, and the fifth compared to $0.05/5 = 0.010$. Results from analyses of all other secondary endpoints and subgroup analyses will not be evaluated relative to statistical significance.

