9.3 Primary Analysis Methods

For the primary analysis, the change from baseline in epistaxis severity score after 24 weeks of study drug administration will be compared between the pomalidomide and placebo groups using a longitudinal general linear model, often referred to as a mixed model for repeated measures (MMRM) (Davis SM 2014), using the MITT population.

The observed change from baseline score at each scheduled post-baseline visit (Weeks 4, 8, 12, 16, 20, and 24 and 4-weeks post-treatment) is the dependent variable. For the purposes of this analysis, study visit will be treated as a categorical repeated measure. The model will include fixed effects for treatment group, study visit, and interactions between those variables and will include the baseline ESS score as a covariate. The model will also be adjusted for the design effect of stratification by pooled site. A heterogeneous Toeplitz covariance pattern will estimate the variance-covariance of the

within-subject repeated measures (study visit), and the Kenward-Roger method will be used to calculate denominator degrees of freedom. Estimates, p-values and 95% confidence intervals will be presented for treatment group comparisons at each visit. In an intent-to-treat fashion, all data will be included in the primary model, regardless of the treatment actually taken by the patient.

The 20 patients with 12-week post-treatment assessments will be included with all 4-week post-treatment assessments.

Treatment group comparisons of the change in ESS score averaged over the week 16, 20, and 24-week visit assessments (a secondary outcome) will be assessed via estimate and contrast statements within this model.

Sample SAS code for the primary model is as follows:

```
proc mixed covtest;
  where VISIT in ("C1","C2","C3","C4","C5","C6","EOS");
  class subject sitenum trtgp VISIT;
  model DELTA_ESS = ESS_BL sitenum trtgp VISIT trtgp*VISIT / ddfm=kenwardroger;
  repeated VISIT / subject=subject type=toeph R rcorr;
  title "Mixed model for change from baseline ESS";
  lsmeans trtgp*VISIT / cl pdiff=all;
run;
```

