9.6 Formal Interim Efficacy Analysis

We will perform a formal interim analysis to evaluate for early overwhelming efficacy based on the change in ESS score from baseline to 24 weeks after 50% and 75% of subjects have completed the 24-week visit or discontinued the study. Futility will also be assessed at 75%, and each formal interim analysis will include a full DSMB safety review.

For assessing early efficacy, the significance level for the interim and final analysis will be based on Lan-DeMets α -spending functions with O'Brien-Fleming boundaries in order to maintain the study-wise α level at 0.05. The α level will be 0.0031 at 50%, 0.0183 at 75% and 0.0440 at the final analysis. The exact α level at the interim will be determined using Lan-DeMets α -spending functions based on the actual percent of data available at the interim.

Assuming 90% power at the end of the study, there is a 26% chance of meeting the stopping boundary at the 50% interim, and a 69% chance at the second interim. If the study actually has 80% power (for example, due to higher-than-expected discontinuation rate or ESS standard deviation), then there is a 54% chance of meeting the stopping boundary at the second interim. Conversely, if the study actually has power $> 95\%$ (for example if treatment group difference in ESS change is 1.2 rather than 1.0 or lower than expected standard deviation), then the chance of stopping is 41% at the first interim and 84% at the second interim.

Futility will be assessed at 75% based on conditional power of the primary efficacy variable. The DSMB may recommend study stop due to futility if the upper limit of the 80% confidence interval for conditional power does not exceed 50%.

With our planned enrollment rate, we expect approximately 6 months of randomization visits to take place after the 50% interim analysis, and so there is a potential to decrease the overall study sample size in the event that the DSMB recommends stopping enrollment based on the interim analysis results. If enrollment proceeds as planned, then randomization will be essentially complete by the time of the 75% interim analysis. In this case, we will request the DSMB to skip the second interim analysis in order to maximize the alpha level at the end of the study. Otherwise, if enrollment is slower than expected, then the results of the second interim analysis still provide a chance to decrease the study sample size.

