Both interim analyses were carried out. Details are provided in **Appendix 2** and **Appendix 3**.

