As of the database snapshot, there were **86** participants that met the criteria for inclusion in the interim efficacy analysis, which is **54%** of the total 159 planned sample size. Using Lan-DeMets α -spending functions with O'Brien-Fleming boundaries in order to maintain the study-wise α level at 0.05 based on the 2 planned interim analyses, the revised alpha level for the 54% initial interim is **0.0046**. The alpha level at the other 2 timepoints is now 0.0179 at 75% and 0.0439 at the final analysis.

Pooled Site

The statistical efficacy analysis adjusts for pooled site. For the interim analysis, sites with fewer than 10 participants will be pooled together with another site such that the new pooled site is not larger than the largest non-pooled single site. Sites with the smallest enrollment numbers will all be pooled together, and sites with moderately small numbers will be pooled with sites that are geographically similar.

The pooled sites for the interim analysis are as follows:

- Pooled small sites (n=14): Cleveland Clinic (n=4), Johns Hopkins (n=4), UCSF (n=2), Utah (n=4)
- Pooled moderately small sites (Midwest) (n=19): Wisconsin (n=7) pooled with Mayo (n=12)
- Non-pooled sites: MGH (n=28), UNC (n=15), Penn (n=10).

Tables and Figures

The efficacy interim analysis will be submitted to the DSMB with a full regular safety DSMB report. The safety DSMB report tables and figures include all available data for all randomized participants. Because this analysis population is different, a few DSMB displays will be repeated for the interim analysis using the interim analysis MITT population.

The following displays will be included in the interim efficacy analysis based on the interim analysis MITT population:

- CONSORT diagram
- Demographics table
- ESS table, showing change from baseline at each visit C1-C6, the average of C4, C5, and C6 and at the post-treatment follow-up visit. Model estimates, confidence intervals and p-values of the differences between treatment groups for the change from baseline at each timepoint will be provided. The model will be fitted based on the model provided in SAP Section 9.3. The primary p-value to be assessed for early study stopping (relative to the significance level of 0.0046) is the comparison between treatment groups at the c6 (week 24) visit. P-values for all other timepoints are purely descriptive.

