As of the database snapshot, there were **127 participants** that met the criteria for inclusion in the interim efficacy analysis, which is **80%** of the total 159 planned sample size. Using Lan-DeMets α -spending functions with O'Brien-Fleming boundaries in order to maintain the study-wise α level at 0.05 based on the 2 planned interim analyses, the revised alpha level for the 54% initial interim was 0.0046, and the revised alpha level is now **0.0230 at 80% and 0.0425 at the final analysis**.

Futility

Futility for the primary efficacy outcome will be assessed by conditional power assuming the remaining outcome data to be collected will be similar to the data that has been collected thus far and not necessarily match the originally hypothesized difference. As stated in the protocol, the DSMB may recommend study stop due to futility if the upper limit of the 80% confidence interval for conditional power does not exceed 50%.

Conditional power will be calculated as follows:

$$ProbNorm \left\{ \left[\sqrt{\frac{(1-P)}{P}} + \sqrt{\frac{P}{(1-P)}} \right] Z - \frac{Z_\alpha}{\sqrt{1-P}} \right\}$$

where $Z = (\hat{T} / SE)$

- probnorm = the **lower** 1-sided alpha value corresponding to the Z value of the formula in the curly brackets based on a normal distribution with mean of zero and standard deviation of 1, denoted $N(0,1)$. We are using the lower tail because if the difference is calculated as placebo – pomalidomide, the Z will be negative if there is a treatment effect, corresponding to a greater decrease in the ESS score for pomalidomide than placebo
- p= the percentage of data available at the interim analysis (**=0.80**)
- Z_α = critical value for the one-sided alpha at the end of the study (**= -2.0286**, corresponding to Z for alpha = **0.0425/2**). If the difference is placebo – pomalidomide, the Z will be negative, corresponding to a greater decrease in the ESS score for pomalidomide than placebo
- \hat{T} is the estimate of the treatment group difference (placebo-pomalidomide) from the MMRM model at C6
- SE is the standard error of the estimate of the treatment group difference from the MMRM model at C6

The 80% confidence interval for the conditional power is calculated as:

$$ProbNorm \left\{ \sqrt{\frac{(1-P)}{P}} \times (Z \pm Z_\gamma) + \sqrt{\frac{P}{(1-P)}} \times Z - \frac{Z_\alpha}{\sqrt{1-P}} \right\}$$

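### The protocol promises reporting adjusted for the interim looks, but the SAP adjusts only the significance threshold, so its 95% CI does not match the 0.0425 test

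*Protocol*

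**What the plan says.** Protocol 10.1 lists four things that the SAP must fix for the interim and final analyses: the endpoints considered, the decision criteria, the handling of changed timing, and bias-adjusted inference. On the fourth it says that "the SAP will specify the method for reporting of trial results that will adjust for the bias that is introduced by the interim analysis".

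The SAP delivers the first three. SAP 9.6 gives the planned levels ("level will be 0.0031 at 50%, 0.0183 at 75% and 0.0440 at the final analysis") and records that "Both interim analyses were carried out". SAP Appendix 2 (interim at 50%) covers the first look, taken at 86 of 159 participants (54%), with level 0.0046; it adds that "The alpha level at the other 2 timepoints is now 0.0179 at 75% and 0.0439 at the final analysis". SAP Appendix 3 covers the second look, taken at 127 of 159 (80%), and resets the levels to "0.0230 at 80% and 0.0425 at the final analysis". SAP 7.7 carries this into the primary test: "This changed the significance level for the primary outcome from 0.044 to" 0.0425.

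For reporting, SAP 9.3 says: "Estimates, p-values and 95% confidence intervals will be presented for treatment group comparisons at each visit". SAP 7.1 adds that "All statistical tests will be 2-tailed" and sets 95% intervals for linear-model estimates. No adjusted estimate, p-value or interval appears in SAP 7.7, 9.3, 9.3.1, 9.6, 11 or the interim appendices. SAP 12 states that nothing was changed from the protocol.

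**The concern.** A lower threshold protects the accept-or-reject decision. It does not alter the point estimate, p-value or interval that readers will quote, and protocol 10.1 lists decision criteria and adjusted reporting as separate items. The fourth item is therefore undelivered, and SAP 12 does not say so.

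Two things are at stake. The 95% interval and the 0.0425 test can disagree on the primary endpoint, which is also the gate to all five key secondary endpoints. And an estimate taken under a stopping rule is biased to some degree, by an amount the reader cannot judge unless an adjusted figure stands beside it.

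**Working it through.** **Inputs.** Looks at 0.54, 0.80 and 1.00 of 159, with nominal two-sided levels 0.0046, 0.0230 and 0.0425 (SAP 7.7 and the interim appendices). Difference 1.0, SD 1.7, 96:48 with data after 10% discontinuation (protocol 10.5). These are design values, not results.

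**1. Reproduce the plan's levels.** O'Brien-Fleming-type Lan-DeMets spending with half the alpha on each side is α(t) = 4[1 − Φ(2.2414/√t)].
- t = 0.54: 4[1 − Φ(3.050)] = 0.0046.
- t = 0.80: 4[1 − Φ(2.506)] = 0.0244 cumulative.
- t = 1: 0.0500.

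Solving for the boundaries by numerical integration gives |z| = 2.836, 2.274 and 2.029, that is, nominal 0.0046, 0.0230 and 0.0425. The planned 0.0031/0.0183/0.0440 and the intermediate 0.0046/0.0179/0.0439 are also reproduced. Using 127/159 unrounded gives 0.0228 at the second look and leaves 0.0425 unchanged.

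**2. Test against interval.** Overall type I error with 0.0425 at the final look is 0.050. If the final 95% CI is read as the test (|z| > 1.960), it is 0.0564. The gap, about 0.0064, is the null probability of a CI that excludes zero beside a non-significant test. At a true difference of 1.0 this happens in about 0.7 to 1.0% of trials (SD 1.6 to 1.7), and at 0.7 in about 2%.

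Example: the full-information SE is 1.7 × √(1/96 + 1/48) = 0.3005. With z = 2.00, p = 0.0455 and the estimate is 0.601.
- 95% CI: 0.601 ± 1.960 × 0.3005 = 0.012 to 1.190, which excludes zero.
- 95.75% CI: 0.601 ± 2.0286 × 0.3005 = −0.009 to 1.211, which agrees with the test.

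The matching level is 1 − 0.0425 = 95.75%, and the interval is 2.0286/1.960 = 1.035 times as wide.

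**3. Bias of the unadjusted estimate** (2,000,000 simulated trials per row, SD 1.7, stopping whenever an efficacy boundary is met).

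| True difference | Share: stop 1 / stop 2 / final | Mean estimate: stop 1 / stop 2 / final | Mean, all outcomes | Mean, no stop at look 1 | 95% CI coverage |
|---|---|---|---|---|---|
| 0.5 | 0.054 / 0.167 / 0.779 | 1.330 / 0.914 / 0.399 | 0.535 | 0.49 | 94.2% |
| 0.7 | 0.130 / 0.299 / 0.571 | 1.364 / 0.944 / 0.516 | 0.754 | 0.66 | 94.8% |
| 1.0 | 0.348 / 0.414 / 0.239 | 1.434 / 1.005 / 0.651 | 1.070 | 0.88 | 95.0% |
| 1.2 | 0.540 / 0.365 / 0.096 | 1.501 / 1.056 / 0.723 | 1.264 | 0.99 | 95.2% |

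The sixth figure follows from the others; at 1.0 it is (0.414 × 1.005 + 0.239 × 0.651)/(0.414 + 0.239) = 0.88. With SD 1.6 it is 0.86.

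**4. What adjusted reporting would show**, taking stage-wise ordering as one example.

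| Look | z | p, unadjusted | p, adjusted | Estimate, unadjusted | Median-unbiased estimate |
|---|---|---|---|---|---|
| Final | 2.029 | 0.0425 | 0.0500 | 0.610 | 0.597 |
| Final | 2.5 | 0.012 | 0.028 | 0.751 | 0.697 |
| Final | 3.0 | 0.003 | 0.025 | 0.902 | 0.748 |
| Second | 2.274 | 0.0230 | 0.0244 | 0.764 | 0.760 |
| Second | 3.0 | 0.0027 | 0.0062 | 1.008 | 0.974 |

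At the final boundary the adjusted 95% CI is 0.000 to 1.190, against 0.021 to 1.199 unadjusted. At the first look nothing changes.

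**The case against.** **The SAP follows the protocol's own analysis section.** This stands. The reporting sentence in SAP 9.3 also appears in protocol 10.4.2, and protocol 10.4.1 sets 95% intervals. The tension lies within the protocol, between 10.1 and 10.4, and the SAP inherits it. A reader might infer that the SAP introduced the 95% CI against the protocol; it did not. What the SAP leaves undone is the item that 10.1 assigns to it.

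**Error control is already handled.** This also stands. A reader might infer that the primary significance decision is unsafe. It is not: the levels reproduce, overall type I error is 0.050, and a stage-wise p below 0.05 at the final look is the same decision as an unadjusted p below 0.0425.

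**The effect would not be overstated here.** Largely right. The average of 1.07 is driven by stops at the first look. A second look was taken, so under the stopping rule as modelled that branch is closed, and the remaining outcomes average too low. A median-unbiased estimate is lower still at the final look, so it does not repair that conditional bias. Overstatement remains possible at a second-look stop with a smaller true effect (0.944 for a true 0.7).

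**Stage-wise ordering is only one choice.** Right. For a final z of 3.0 it gives p of about 0.025, ordering by estimate about 0.010, and ordering by z about 0.0045. The protocol names none, which is a reason to name one before unblinding and not a reason to name none.

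**Conclusion.** The concern holds as an undelivered reporting commitment, together with an interval that does not match the primary test. The primary test is sound.

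The size is modest. Averaged over all outcomes, the unadjusted estimate is about 0.04 to 0.07 ESS points too large for true differences of 0.5 to 1.2, against the minimally important difference of 0.7 cited in protocol 10.5. Overall coverage is about 94 to 95%. The CI and test disagree in about 0.6 to 2% of trials under the null and at true differences of 0.7 and 1.0. The documents do not support a general claim that the headline effect will be exaggerated.

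These figures assume the design SD and missingness, information proportional to participant counts, and stopping whenever an efficacy boundary is met, although the SAP says only that the DSMB may recommend it. The final site counts in SAP 7.6 sum to 24 + 51 + 21 + 16 + 12 + 21 = 145, not 159. A reader might infer an early stop, but the documents give no reason. If 145/159 were the final information, keeping 0.0425 would be slightly conservative (overall 0.0475).

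**What to change.** Before unblinding:

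1. In SAP 9.3, for the week-24 primary contrast, present beside the MMRM result a named group-sequential adjusted estimate, CI and p-value, for example median-unbiased under stage-wise ordering, based on the looks actually taken. State the final information fraction and how data collected after the second look enter.
2. At minimum, report a 95.75% CI for that contrast so that interval and test agree.
3. If no adjusted inference is given, declare the departure from protocol 10.1 in SAP 12, with the reason.

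The cost is a paragraph of SAP text and one post-processing step that uses the week-24 estimate, its SE and the boundaries already in the appendices. No new data or design change is needed. The CI becomes slightly wider (3.5% for the 95.75% interval) or the reported p-value larger.
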